7.1 Ethical Considerations: Informed Consent/Accent and HIPAA Authorization

The study will be conducted in accordance with the ethical principles that have their origin in the Declaration of Helsinki. No deception will be involved and there is no payment to participants. Only the minimal data necessary to complete the study will be obtained and age information will be binned help blind it. No direct subject indicators will be listed.

It is conceivable that potential new observation of anosmia in SARS-CoV-2 negative patients, may suggest a possible underlying condition, such as Alzheimer's or Parkinson's Disease (or head trauma), which may merit further testing by more in-depth tests. If so the olfactory test may be added to the record. The data will be flagged in EPIC for potential follow up and consideration by the patient's primary physician. The PI of the clinical trial team is **[name], MD who is a Yale Associate Professor of Rhinology and Endoscopic Skull Base Surgery** and is Yale's expert in olfaction and he could be consulted about the most appropriate follow up.

7.2 Institutional Review Board (IRB) Review

The protocol will be submitted to the IRB for review and approval. Approval of the protocol must be obtained before initiating any research activity. Any significant change to the protocol or study team will require an approved IRB amendment before implementation. The IRB will determine whether informed consent and HIPAA authorization are required. In addition:

- The IRB will conduct continuing review at intervals appropriate to the degree of risk, but not less than once per year.
- A study closure report will be submitted to the IRB after all research activities have been completed.
- Other study events (e.g. data breaches, protocol deviations) will be submitted per Yale IRB's policies.

7.3 Subject Confidentiality

Subject confidentiality is held in strict trust by the research team. Subject medical record review will be limited to the just the elements needed to complete the study, which includes age, gender and results of the COVID test. Only authorized HIPAA and CITI trained (if applicable) study team members will be allowed to extract research data from medical records and enter it into our research database. No direct subject identifiers will be entered into the research database.

Each subject will be assigned a unique study number. A master list linking the unique study number to the human subject will be maintained in a locked drawer in [name] office.

7.4 Deviations/Unanticipated Problems

If the study team becomes aware of an anticipated problem (e.g. data breach, protocol deviation), the event will be reported to the IRB by an email from [name].

7.5 Data Collection

Data will be collected for outpatients during the drive up test. It will be digitalized (by camera) and manually entered into a spreadsheet. Asymptomatic test results will be collected in a similar fashion. Physical records will be destroyed at the end of the study. All data will be de-identified and de-linked.

7.6 Data Quality Assurance

Good Clinical Practice is followed and will be further overseen by [name], MD (Chief, Yale Section of Otolaryngology). Should there be any deviations in the PCR data we will use the Connecticut State Testing Laboratory and we have already spoken at length to **[name]., HCLD (ABB), Laboratory Director Connecticut Department of Public Health** and he would be delighted to do any secondary testing and insure that our testing and data quality meets the highest bar.

7.7 Study Records

The key documents considered in the study records include the protocols, consents forms, case report forms, subject medical records (EPIC), and surveys.

7.8 Access to Source

The source document (Consent form and multiple choice answers) will be entered into EPIC. The PI will have access to the source documents.

7.9 Data or Specimen Storage/Security

Outpatient data will be collected, by hard copy, digitalized and stored and maintained in a secure manner by password protection.

7.10 Retention of Records

The study records will be retained for at least 3 years after the study is closed, and up to 6 years if any personal health information is connected to the records. If permission is needed to move or destroy the records, we will identify the person who will need to be contacted (investigator, sponsor, etc.).

7.11 Study Monitoring

[name], MD (Chief, Yale Section of Otolaryngology) will monitor the study.

7.12 Data Safety Monitoring Plan

There are minimal risks associated with this non-invasive olfactory device with no risk to subject. No children will be involved.

7.13 Study Modification

If there are any significant study modifications either due to poor performance or a special opportunity the IRB will be contacted. Changes in the protocol will be highlighted and if approved they would be acted upon. We note that as this is a non-invasive device any risk to the patient will be minimal, thus this may not require review of the entire IRB panel, rather a subset.

7.14 Study Discontinuation

The asymptomatic element of study may be discontinued if no differences are seen in olfactory performance of COVID-19+ asymptomatics compared to their COVID-19- counterparts.

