5.3.1 Number of Participants

Upon consultation with Yale biostatisticians Profs. [name] and [name], based on our sampling they calculated the following table to show the precision of sensitivity/specificity measurements for different sample sizes (**Table 1**). For example, the 95% confidence interval for 90% sensitivity with 100 subjects ranges from 82 to 95% , but if we have 400 subjects, the confidence interval ranges from 87 to 93% (about +/- 3%). Thus the number of participants will be guided by statistical analysis of the data. A minimal estimate is ~100 outpatients that are SARS-Co-V2 positive so as to have good confidence

intervals. Here we presume to have at least 100 age/gender matched SARS-Co-V2 negative subjects. If there are 3:1 SARS-Co-V2 negative to SARS-Co-V2 positive then ~400 outpatients (300 +100) will be tested. For the more exploratory testing with asymptomatics

Sens/Spec	Sample Size for Denominator*						
	100	150	200	250	300	350	400
0.50	0.20	0.17	0.14	0.13	0.12	0.11	0.10
0.60	0.20	0.16	0.14	0.13	0.11	0.11	0.10
0.70	0.19	0.15	0.13	0.12	0.11	0.10	0.09
0.80	0.17	0.13	0.12	0.10	0.09	0.09	0.08
0.90	0.13	0.10	0.09	0.08	0.07	0.07	0.06

we will limit the study to ~100 COVID-19 positive subjects and a similar number of SARS-Co-V2 negative subjects.

Table 1: Sample Size Calculations (Width of a 95% confidence interval around the proportion).

*Denominator is those that are COVID+ for sensitivity and those that are COVID- for specificity

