 - a. [Alternative should there be any issues with the camera or the patient must get out of the car]: The patient will take the completed test packet, place it back in the pouch and under the windshield. The HCW will take the packet and remove the **Consent Form** and **Multiple choice questionnaire form**, check if it is completed (if ask the patient), and place all remaining materials in a biohazard box for destruction. The Consent form and the Questionnaire will be digitalized (scan or photographed) and linked with EPIC so as to be compared to the PCR test results.
4. Information from the uploaded and **Multiple choice questionnaire form** will be entered by a person authorized to access the information into a table that includes:
 - a. Unique identifier
 - b. Gender
 - c. Age band (10 year)
 - d. Y/N to patient self-identified new loss of smell or taste
 - e. Y/N to patient response to "things in the last year smell different"
 - f. Y/N to patient self-identified blocked or stuff nose
 - g. Individual answers on the 5 window smell test
 - h. RT-PCR results for SARS-CoV-2 (+, - or Inconclusive)
 - i. Any other tests for COVID19 (CT or Serological) if given
5. The data will be analyzed in the following fashion:
 - a. Patients that report a blocked or stuffy nose will be excluded from the main analysis (as COVID-19 loss of smell is not due to nasal congestion); but will be analyzed separately to see how this would confound any interpretation.
 - b. Patients that are denoted SARS-CoV-2 "inconclusive" will be excluded from the main analysis; but will be separately analyzed to see if they colocalize with normosmia or anosmia.
 - c. Patients will be split into SARS-CoV-2 positive and negative. As the negative pool is likely to be much larger it will be statistically matched by gender and age profile (potentially with larger bands – e.g. 20 year, depending on the sample size)

- d. The + and - SARS-CoV-2 groups individual performance on the smell test (score 0-5) will be plotted as a histogram. A cutoff will best be chosen to segregate people with normosmia and anosmia (e.g. score = 2 or 3).
- e. False Positives (FP) and False Negatives (FN) will be identified and used to measure the selectivity and sensitivity, respectfully.
- f. Based on the statistical performance (see Table 1) we will determine when we have enough patients to complete the study with a given value of precision.

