- g. If a subject fails the smell test (hyposmia or anosmia) but is SARS-CoV-2 negative, yet has other symptoms suggesting being positive for COVID19, we will consider re-testing the subject in 2-3 days by the PCR or serological assay in case the loss of smell precedes a PCR result, or the loss of smell extends past the point in which the viral titer is low and no longer picked up by PCR and would instead be detected by an antibody.

6. The treatment of asymptomatic people will follow an identical protocol with the following differences:
 - a. The study group would consist of high risk subjects that are determined to be positive to SARS-CoV-2 (yet asymptomatic) and the control group would be SARS-CoV-2 negative subject of matching age and gender.
 - b. The smell kit will be directly given to the subject and for HCW the test can be performed at their home.
 - c. There will be a variation of the test in which the order of the scents is altered so that the HCW subject can be re-tested.
 - d. The initial sample size is smaller as this study would firstly see if there was a significant increase of the fraction of anosmia or hyposmia subjects in COVID19+ asymptomatic individuals.

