6.4.2 Sample Size Considerations

Upon consultation with Yale biostatisticians Profs. [name] and [name], based on our sampling they calculated the following table to shows the precision of sensitivity/specificity measurements for different sample sizes (Table 1). For example, the 95% confidence interval for 90% sensitivity with 100 subjects ranges from 82 to 95% , but if we have 400 subjects, the confidence interval ranges from 87 to 93% (about +/- 3%). Thus the number of participants will be guided by statistical analysis of the data. A minimal estimate is ~100 outpatients that are SARS-Co-V2 positive so as to have good confidence intervals. Here we presume to have at least 100 age/gender matched SARS-Co-V2 negative subjects. If there are 3:1 SARS-Co-V2 negative to SARS-Co-V2 positive then ~400 outpatients (300 +100) will be tested. For the more exploratory testing with asymptomatics we will limit the study to up to 250 HCW. If the results are encouraging with a loss of smell in asymptomatic the sample size could be increased to increase the precision, as done in the outpatient cohort.

Table 1 (replicated from before): Sample Size Calculations (Width of a 95% confidence interval around the proportion).

*Denominator is those that are COVID+ for sensitivity and those that are COVID- for specificity

Sens/Spec	Sample Size for Denominator*						
	100	150	200	250	300	350	400
0.50	0.20	0.17	0.14	0.13	0.12	0.11	0.10
0.60	0.20	0.16	0.14	0.13	0.11	0.11	0.10
0.70	0.19	0.15	0.13	0.12	0.11	0.10	0.09
0.80	0.17	0.13	0.12	0.10	0.09	0.09	0.08
0.90	0.13	0.10	0.09	0.08	0.07	0.07	0.06

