6.4.3.2 Secondary Objectives Analyses

Potential loss of smell in asymptomatics will be compared to the presence of SARS-CoV-2 coronavirus, as determined by RT-PCR. For the more exploratory testing with asymptomatics we will limit the study to ~250 HCW, with focus on the sensitivity and specificity and if in short longitudinal testing there is an acute loss of smell. If the results are encouraging with a loss of smell in asymptomatic subjects the sample size may be increased to improve the precision, as done in the outpatient cohort.

Safety

No safety issues to report as this is an observational trial.

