6.4.3.4 Interim Analysis

Not applicable

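### Asymptomatic cohort: 6.4.3.4 rules out an interim analysis, but 7.14, 6.4.2 and 6.4.3.2 let outcome data stop or enlarge the cohort with no timing or criterion, and the number of PCR positives is not fixed.

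*Combined protocol and SAP*

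**What the plan says.** **Stopping and enlarging.** Section 7.14 says that the asymptomatic element "may be discontinued if no differences are seen in olfactory performance of COVID-19+ asymptomatics compared to their COVID-19- counterparts". Section 6.4.2 says: "If the results are encouraging with a loss of smell in asymptomatic the sample size could be increased to increase the precision". Section 6.4.3.2 repeats this almost word for word. Both compare the enlargement with what is done for outpatients, where step 5f of section 6.3 says, with reference to Table 1, that "we will determine when we have enough patients to complete the study with a given value of precision".

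**Staging.** Step 6d of section 6.3 says: "The initial sample size is smaller as this study would firstly see if there was a significant increase of the fraction of anosmia" or hyposmia in asymptomatic positives.

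**Interim analysis.** The whole of section 6.4.3.4 is "Not applicable".

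**Size.** Section 5.3.1 says that for asymptomatics "we will limit the study to ~100 COVID-19 positive subjects and a similar number of SARS-Co-V2 negative subjects". Section 6.4.2 says: "For the more exploratory testing with asymptomatics we will limit the study to up to 250 HCW". The Synopsis and 6.4.3.2 also give about 250 health care workers (HCW), with no split by PCR status. Step 6a and section 6.3.3 describe positives who are already known. Section 5.1.1 describes, at one nursing home, at least 30 known asymptomatic positives (not all of them staff) and about 250 untested employees.

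**The concern.** Stopping for lack of a difference and enlarging on a favourable result both require someone to compare smell results by PCR status and act on them. That is a data-dependent decision about sample size, and the section that should describe it says there is none. Nothing states when the comparison is made, what counts as absence of a difference, or what counts as favourable. Enlargement is justified by precision, but its stated trigger is the result and not the interval width.

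At stake is the study's stated secondary objective: whether asymptomatic positives have a mild smell defect. Section 7.14, followed as written, could close that question while the data still allow a material excess. How likely this is depends on a criterion that is not defined and a number of positives that is not fixed. A reader of the plan also cannot tell how many positives the asymptomatic sensitivity will rest on.

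**Working it through.** **1. The plan's own precision figures.** Clopper-Pearson 95% limits give 82.4 to 95.1% for 90/100 and 86.6 to 92.8% for 360/400, matching the text of 5.3.1 and 6.4.2. The same method reproduces 34 of the 35 cells of Table 1 (the exception is 0.60 at n = 250: 0.1248 against a printed 0.13). The Table 1 footnote makes positives the denominator for sensitivity, so their number governs precision.

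**2. How many positives?**
- Chosen by PCR status: 100 + 100 = 200, which fits under the cap of 250.
- Unselected HCW: 100 positives among 250 needs 100/250 = 40% positive. The documents give no positivity rate. At an assumed 10% or 20%, 250 HCW yield 25 or 50 positives.
- The 30 + 220 split used below is an assumption. It takes the 30 known positives of 5.1.1 as the number reached, and 250 - 30 = 220 negatives.

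**3. Chance of finding no difference when there is one.** Let X be the number with smell loss among n1 positives and Y the number among n0 negatives, independent binomials. Loss rates are assumed: 10% in negatives, and 20%, 30% or 50% in positives. The binomial probabilities of all (X, Y) outcomes that meet the criterion are summed.
- Reading A: X/n1 is no higher than Y/n0.
- Reading B: no significant excess in positives (two-sided 5% Fisher test).

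| Positives + negatives | A: 20% / 30% / 50% | B: 20% / 30% / 50% |
|---|---|---|
| 100 + 100 | 0.03 / <0.01 / <0.01 | 0.56 / 0.065 / <0.01 |
| 50 + 200 | 0.05 / <0.01 / <0.01 | 0.56 / 0.10 / <0.01 |
| 30 + 220 | 0.09 / 0.01 / <0.01 | 0.68 / 0.24 / <0.01 |

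These rows total 200 or 250, so they describe the full planned cohort. A look at half that size (assumed) does worse at 20% loss: by the same sum, 50 + 50 gives 0.10 (A) or 0.81 (B), and 15 + 110 gives 0.18 or 0.81.

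**4. What an observed tie leaves open.** With 10% observed in both groups, the Newcombe upper 95% limit for positive minus negative is √[(u1 - p1)² + (p0 - l0)²], where u1 and l0 are Wilson limits.
- 10/100 v 10/100: √[(0.174 - 0.10)² + (0.10 - 0.055)²] = 0.087, about +9 points.
- 3/30 v 22/220: √[(0.256 - 0.10)² + (0.10 - 0.067)²] = 0.160, about +16 points.

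**5. Bias from enlarging on the result.** At 30 + 220 with true loss of 20% in positives, the mean observed loss in positives, given a significant first result, is 0.277. Pooled with 70 further positives: (30 × 0.277 + 70 × 0.20)/100 = 0.223. The bias is small.

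**The case against.** Several points on the other side stand.

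- **Where the look falls.** A reader might infer that step 6d sets up a look part-way through the 250. The documents do not say so. Step 6d is in a list of differences from the outpatient protocol, so its smaller initial sample may only mean smaller than the roughly 400 outpatients. The look could come at 250, with enlargement considered afterwards.
- **Sizing.** A reader might infer that about 100 positives and about 250 HCW contradict each other. They do not if subjects are chosen by PCR status, as step 6a and 6.3.3 suggest. What is unsettled is whether they are so chosen.
- **Meaning of the probabilities.** They come from the full planned cohort and are not the operating characteristics of a defined interim stop.
- **Consequence.** The cohort is called exploratory and no confirmatory test is specified. The wording is permissive, and 7.2 and 7.13 send significant changes to the IRB. A stop for lack of a difference does not by itself inflate false positives.

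None of this removes the conflict. Permissive wording and IRB review supply no statistical criterion. If the look comes at 250, 6.4.3.4 should say so, and 7.14 still needs a definition.

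**Conclusion.** The inconsistency is real and should be corrected, but it is limited to the secondary asymptomatic cohort; it does not touch the primary outpatient analysis. Section 6.4.3.4 denies a look that 7.14, 6.4.2 and 6.4.3.2 rely on, and neither its timing nor its criterion is stated.

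With assumed loss of 10% in negatives and 20% in positives, 30 positives and 220 negatives give a 0.09 or a 0.68 chance of finding no difference, depending only on how that phrase is read. With 100 and 100 the figures are 0.03 and 0.56. The loss rates and the 30 + 220 split are assumptions.

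It would be tempting to conclude that 7.14 could hide a large effect. The figures do not support that: at 50% loss in positives, the chance is below 0.01 in every split tabulated. The exposure is to a mild defect, which is what the secondary objective is about.

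**What to change.** 1. **6.4.3.4:** replace the current entry with a statement that asymptomatic data will be examined for the decisions in 7.14, 6.4.2 and 6.4.3.2. State when, and whether this is before or at about 250.
2. **7.14:** treat the result as showing no difference only if the upper 95% confidence limit for the difference in smell loss (positive minus negative) is below a margin stated in advance. If the cohort ends without meeting this, report it as inconclusive, with the number of positives.
3. **6.4.2 and 6.4.3.2:** trigger enlargement on interval width, as in Table 1. Otherwise report that enlargement followed a look at outcome data, and show initial and added subjects separately.
4. **Synopsis, 5.3.1, 6.4.2 and 6.4.3.2:** use one sizing basis. State whether subjects are chosen by PCR status and whether the matched negatives are inside the 250. If HCW are unselected, replace the figure of about 100 positives with the expected range and add Clopper-Pearson widths at 0.50 / 0.90: n = 25, 0.41 / 0.27; n = 30, 0.37 / 0.24; n = 50, 0.29 / 0.18 (n = 100 in Table 1: 0.20 / 0.13). Where 0.50n or 0.90n is not whole, the width is interpolated.

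**Cost.** The changes are to wording, and the stated precision may become less favourable. No extra subjects are requested. The rule in item 2 will seldom be met with few positives, so the cohort may run to its cap more often. If true loss is 10% in both groups, 30 + 220 would meet it 22%, 47% or 73% of the time at assumed margins of 10, 15 or 20 points. The sponsor should choose the margin with this in view.

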7.15 Study Completion

We anticipate completion by ~3-6 weeks after the IRB is approved, and when done the IRB will be notified. The exact timing will depend on how quickly the data is collected and the incident rate of COVID-19 in the population.

7.16 Conflict of Interest Policy

There is no link of this study to the pharmaceutical industry. We disclose that [name] founded and has related intellectual property in 'u-Smell-it, LLC', the company that has developed the u-Smell-it™ olfactory testing device that is being evaluated in this COVID-19-related clinical trial. Due to these COI he is not be an investigator on the IRB protocol and is not participating in the study apart from supplying the test devices to [name]. For transparency the PI, [name], has no financial ties or intellectual property associated with 'u-Smell-it, LLC'

7.17 Funding Source

There is no funding required for this very brief study as the olfactory test cards have already been obtained and will be given at no charge from 'u-Smell-it LLC'.

7.18 Publication Plan

We anticipate publication of these findings in a prominent journal. [name] will hold the primary responsibility for publishing the study results.

8 Appendices

Appendix #	Title	Section	Topic

Protocol Number

Version Date and Version #
